## 7.2 End of Study Definition

End of study will occur when 20 subjects have completed this pilot project.

## 8.0 SUBJECT SELECTION

### 8.1 Inclusion & Exclusion Criteria

Eligibility will be determined by inclusion and exclusion criteria below and confirmed by medical record review as necessary.

#### Inclusion Criteria

1. Age ≥50-90 years
2. Willing and able to undergo all procedures
3. Retains decisional capacity at initial visit
4. Meets criteria for MCI, amnestic type (Petersen, 2004).

#### Exclusion Criteria

1. Significant kidney injury requiring hemodialysis
2. Automatic Internal Cardiac Defibrillator (AICD) or Pacemaker
3. Significant congestive heart failure
4. History of clinically significant ischemic or hemorrhagic stroke, or lacune or infarct considered by radiologist likely to cause or contribute significantly to cognitive symptoms
5. History of thalamic lacunar stroke
6. Modified Hachinski Ischemia Score >4 points
7. History of seizure disorder requiring medication
8. History of brain surgery (for seizure disorder, aneurysms, or benign/malignant tumor)

9. History of HIV/AIDS
10. Severe untreated obstructive sleep apnea
11. Greater than three servings alcohol daily or illicit drug use
12. Major neurologic disorders other than dementia (e.g., MS, ALS)
13. Schizophrenia, bipolar disorder, other serious mental illnesses
14. Other significant medical conditions at investigators' discretion
15. Pregnancy
16. Lack of study partner (Participants are allowed to find a new study partner if the original study partner withdraws)

## 8.2 Vulnerable Populations

The consent process is conducted as a face-to-face interview with the patient. No study procedures are initiated until the consent process is complete. In all cases, prospective participants with dementia will first be assessed for their ability to provide informed consent.

The subject must provide consent himself/herself at screening. We will not enroll any participant deemed to have impaired decisional capacity. Participants will be consented at the study sites involved using local procedures established by the individual sites.

If any participant appears to have cognitive impairment when they return for their follow up visit, capacity to give consent will be assessed in clinical interviews of participants by clinicians experienced in clinical dementia research. If it is found the subject no longer has capacity to consent, the Legally Authorized Representative will provide consent if appropriate.

## 8.3 Subject Identification

### Self-Identification

Potential subjects may self-identify by responding to IRB-approved recruitment efforts, such as web postings, posters/flyers, radio or TV ads, newspaper ads, mass mailings, email blasts, etc. IRB-approved screening scripts, eligibility questionnaires, and email response templates will be utilized when communicating with potential subjects who respond to these recruitment methods. Information collected from the potential subject is to be limited to protect the potential subject's privacy and information collected from potential subjects who fail pre-screening will be destroyed.

### Identification in Clinical Practice

Potential subjects may be identified during routine visits to the Memory Disorder's Clinic in the Neurology Clinic at the Froedtert and the Medical College of Wisconsin (MCW), Middleton VA Hospital Madison, Memory Assessment Clinic [University of Wisconsin (UW) Hospital and Clinics' Memory Clinics and the Wisconsin Alzheimer's Institute (WAI) Diagnostic Clinic Network, a group of diagnostic clinics associated with the WAI experienced in diagnosing and recruiting patients with Mild Cognitive Impairment and Alzheimer's disease. A member of the clinical team will inform potential subjects of the research opportunity and provide an IRB-approved consent form. Potential subjects will be pre-screened through medical record review and conversation with the subject using an IRB-approved script. Information collected from potential subjects who fail pre-screening will be destroyed. Potential subjects who meet all pre-screening criteria will be invited for a formal screening/baseline visit.

## **Department Database**

The Wisconsin ADRC Recruitment Registry, described under a separate UW-Madison protocol (2011-0772) may be used to identify eligible subjects.

### **8.4 Subject Recruitment**

A total of 20 subjects will be recruited from two sites in the United States. Several recruitment strategies may be employed, and sites may use a combination of methods depending on their capabilities. Possible recruitment strategies are as follows (non-comprehensive list):

#### **Recruitment through Clinical Practice**

If the potential subject is agreeable, they will be provided contact information for the study team or the research team will initiate contact.

#### **Posters/Flyers**

Flyers announcing that volunteers are needed for a study may be posted in memory clinics of the Wisconsin Alzheimer Institute, UW Health facilities (including UW Hospital and Clinics, The American Center, South Park clinics), Meriter Hospital, Middleton Veteran's Hospital. Several key details of the study will be included in the flyer (key eligibility criteria, number and length of visits, location of study site, type of remuneration) along with a call back number for people to call in case they are interested.

#### **Telephone Recruitment**

When potential subjects contact the study team, a brief description of the study's purpose and participation requirements will be reviewed. This must also include a statement that participation is voluntary. The screener will ask the caller if s/he has any questions and whether they are interested in participating. After all questions have been answered, the study team member will ask if the potential subject is interested in proceeding to the next step in recruitment for the study (e.g., scheduling a visit to learn more and go through the consent process, or answering some screening questions).

#### **Letters**

UW Madison will utilize the Wisconsin Alzheimer's Disease Research Center (ADRC) recruitment resources to identify individuals who meet inclusion criteria. The ADRC supports researchers in their pursuit to identify answers that will lead to improved diagnosis and care for patients, as well as those seeking a cure and prevention of Alzheimer's Disease. The ADRC can hold the names and eligibility information of potential volunteers, allowing ADRC staff to contact them for appropriate research studies.

The ADRC will send the recruitment letters to eligible individuals which contain the reason for receiving the letter and outlining the procedures and purpose of the study, signed by Drs [name] and [name]. If individuals are interested, they can contact [name] by email or phone.

### **8.5 Remuneration and Retention Strategies**

For subjects making trips of 25 miles or more one way, they will be reimbursed at the standard UW or MCW travel rate. Remuneration will be offered for specific procedures.

MRI: \$50 x 2 scans (\$100)

Neuropsychological Testing: \$50 x 3 evaluations (\$150)

Stimulation: \$20 x 15 sessions (\$300)

Study partners will receive \$25 for baseline and \$25 for both post-treatment follow-up participation. The study partner will receive a total of \$75 if they complete all visits, even if they participate via telephone.

Payments for each completed activity will be processed within 12 weeks from completion.

For MCW subjects only, on a case-by-case basis, subjects may be reimbursed for an overnight stay (up to 5 days per week) in a hotel or other form of lodging if necessary to complete a study visit. If their visit requires an overnight stay, they will receive a \$25 meal reimbursement per night.

To pay subjects, we need their social security number. Any payment may be reportable as income on their taxes.

Subject's enrolled at MCW may be eligible to stay at Kathy's House as an alternative to a hotel or other form of lodging.

### **Kathy's House**

If subjects reside at a permanent address 50 miles or greater from Milwaukee, they may be eligible for lodging at Kathy's House. Kathy's House is located on the Froedtert Hospital campus and provides housing for research subjects who require a stay greater than 3 days.

Each room includes the following:

- Most rooms have both a queen and a single bed
- Private bathroom with walk-in shower
- Bed and bath linens
- Television, small refrigerator, and telephone (local)

While lodging at Kathy's House, guests also have access to the following communal amenities:

- Fully equipped kitchen
- Refrigerator, pantry, and freezer storage space
- Free Wi-Fi
- Living Room
- Dining Room
- 6 interior & 4 exterior lounge spaces
- Fitness Center
- Meditation Room
- Laundry facilities
- Library, including computer workstations

### **Food**

- Guests are responsible for their own meals
- Each room has designated pantry, refrigerator, and freezer storage space in the kitchen
- A meal from a local restaurant is provided once a week.

### **Parking and Transportation**

- Parking is available for guests on a surface lot.
- Complimentary shuttle service is available during the week on a limited basis due to the COVID-19 pandemic.

### Guest Responsibilities

It is important that guests staying at Kathy's House are comfortable in a communal environment. There is no maid service, so guests are asked to clean up behind themselves in the common areas and in their rooms. Rooms are thoroughly cleaned upon guest check-out.

Guests staying at Kathy's House must have a caregiver with them for the duration of their stay. Guests must also be able to perform basic mobility and care functions, including:

- do personal laundry as needed
- plan, prepare and clean up following meals

Payment for lodging at Kathy's House will be arranged and covered by the study team. Care givers are expected to lodge with subjects to the extent possible.

With the subject's verbal consent, a referral can be sent by the study team to Kathy's House. The following personal information will be included in the referral to Kathy's House: subject and care giver name, date of birth, gender, city, state, zip code, phone number, email address, and reason for visit.

Upon reception of the referral, Kathy's House will conduct a formal background check using TruthFinder.com. The subject and caregiver's names and birthdates will be used to check for any criminal charges associated with either person. Kathy's House has the right to reject any referral based on this background check.

[Kathys-house.org](http://Kathys-house.org) provides additional information.

## **8.6 Early Termination and Withdrawal**

Subjects are free to withdraw from participation in the study at any time upon request.

The Principal Investigator (PI) may discontinue or withdraw a subject from the study for the following reasons at his/her discretion:

- Pregnancy
- Subject non-compliance with study requirements (e.g., study intervention non-compliance)
- If any clinical adverse event (AE) or other medical condition or situation occurs such that continued participation in the study would not be in the best interest of the subject
- If the subject is no longer an appropriate candidate for participation
- There is evidence of progressive disease or unacceptable toxicity
- Subject unable to receive scheduled intervention for 3 weeks

Subjects who sign the informed consent form and are randomized but do not receive the study intervention will be replaced. Subjects who sign the informed consent form, are randomized and receive the study intervention, then subsequently withdraw, or are withdrawn or discontinued from the study, will not be replaced.

The following actions should be taken if a subject withdraws, or fails to return for a required study visit:

- The site will attempt to contact the subject and reschedule the missed visit within 6 weeks and counsel the subject on the importance of maintaining the assigned visit schedule and ascertain if the subject wishes to and/or should continue in the study.
- Before a subject is deemed lost to follow-up, the investigator or designee will make every effort to regain contact with the subject where possible, 3 telephone calls and, if necessary, a certified

letter to the subject's last known mailing address or local equivalent methods. These contact attempts shall be documented in the subject's medical record or study file.

- If the subject continues to be unreachable, they will be considered to have withdrawn from the study with a primary reason of lost to follow-up. The withdrawn date is the last day of attempted contact.

The study team will attempt to obtain the following information from subjects following early termination or withdrawal: Adverse events and reason for withdrawal.

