	
 
• Consent rate
 
• ADCS PACC score at 3 and 6 months
 
• Neurite density (intracellular volume fraction) at 3 months
 
• Diffusivity indices: Fractional anisotropy (FA), Mean (MD), Axial (AD), Radial (RD)
 
• Diffusivity at 3 months
 
• Morphometric indices: Cortical thickness, Surface Area, Volume, gyration index at 3 months.
 
• ASL perfusion indices: blood flow, blood volume, mean transit time, time to peak, at 3 months
 

Study Design	The study design is a double-blinded, randomized pilot clinical trial of HD-tDCS/sham HD-tDCS combined with CT, administered to subjects with amnestic MCI (aMCI) in blocks of 5 daily treatments for a total of 15 sessions. There will be one treatment block/month for a total of 3 months. 20 participants with aMCI will be enrolled. There will be 2 treatment groups/arms with 10 subjects per group/arm. We anticipate a dropout rate of appr. 10% and aim to complete procedures in 20 subjects.
Study Intervention	High definition transcranial direct current stimulation (HD-tDCS) Sham HD-tDCS Computerized Cognitive training (CCT) Sham CT
Total Number of Subjects	20
Study Population	Male and females aged 50 to 90 years with established diagnosis of MCI amnestic type. Total of 20 subjects
Statistical Methodology	Given the pilot nature of this study, two feasibility outcomes will be included: Consent rate and treatment completion rate. 20 patients are enough to calculate a 90% exact binomial confidence interval of (.75, 1) if all 20 are observed to complete treatment. Thus, this sample size is large enough to potentially exclude completion rates of 3/4 or lower. The pilot data from this study will provide initial estimates of the variability and the effect sizes. This information will then be used for the formal calculations of power and sample size necessary to conduct a future phase II trial.
Estimated Subject Duration	The duration of the study for each subject is approximately 6 months.
Estimated Enrollment Period & Study Duration	Study enrollment and follow-up will occur over 9 months with the total expected duration of the trial to be 12 months.

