## 5.0 INTRODUCTION

### 5.1 Mild Cognitive Impairment

Mild cognitive impairment (MCI) is currently an area of considerable clinical and research interest because of the high rate of conversion from MCI to Alzheimer disease (AD) (Almkvist et al., 1998; Collie et al., 2000; Kluger et al. 1999; Morris et al., 2001; Petersen et al., 1999; 2001; Rubin et al., 1989; Shah et al., 2000; Wolf et al., 1998). Several studies have demonstrated that patients with MCI progress to AD at a higher rate (10 to 15% per year) than normal elderly patients (1 to 3% per year). Therefore, MCI patients are considered to be at a higher risk for AD. MCI may be classified as either amnestic or non-amnestic, with the primary clinical distinction being the presence of prominent memory impairment in the former, and the predominant involvement of cognitive domains different from memory in the latter. Accordingly, amnestic MCI likely represents a prodromal stage of Alzheimer's dementia (Petersen et al., 2001); it is distinguished by impairment of episodic memory, and when contrasted with normal aging amnestic MCI is associated with a high degree of memory impairment with little or no impairment in activities of daily living (ADLs) (de Leon et al., 1993; Petersen et al., 2001). Individuals with amnestic MCI do not meet the currently accepted clinical criteria for probable AD, but the high rate of conversion from amnestic MCI to AD makes early diagnosis and treatment an important clinical issue. In its earliest stages, AD manifests primarily as cognitive impairment; As AD progresses, there is further loss of cognitive abilities, a loss of functional independence, and the development of behavioral problems (Gauthier, 1998). Early diagnosis and treatment may delay the onset of these symptoms.

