## 10.0 STUDY VISITS AND PROCEDURES

### 10.1 Study Calendar

The procedures performed at each study visit are listed in the table below.

Visit	Baseline	Treatment Period			Month 3	Month 6	Early Withdrawal
	1	2-6	7-11	12-16	17	18	
Visit Window	-6 months		±4 weeks	±4 weeks	Up to 6 weeks post Visit 16	3 months post Visit 16 ± 8 weeks	
Timeframe		Week 1 (Month 1)	Week 2 (Month 2)	Week 3 (Month 3)			
Informed Consent	X						
Review Eligibility Criteria	X						
Demographics	X						
Review Concomitant Medications	X				X		X
Obtain Medical History	X						
Physical Exam	X				X		X
Vital Signs 	X				X		X
Randomization	X						
Study Partner Questionnaires	X				X	X	
Cognitive Battery	X				X	X	
MRI	X				X 		
TMS Neuronavigation (for stimulation planning) MCW only	X						
Device Administration		X	X	X			
Adverse Events Review/Assessment		X	X	X	X	X	X

1 Vitals include: pulse rate, body temperature, blood pressure, respiration rate, height, and weight

2 MRI will aim to be completed within 6 week window, but can be completed up to 12 months after Visit 16 if scheduling problems arise

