### Treatment

#### Visits 2-16\*

At these visits, the following will occur:

- Cognitive training with HD-tDCS treatment OR
- Cognitive training with sham HD-tDCS treatment
- On Mondays prior to CT and Fridays after CT, subjects will be assessed on competency and ability to perform the CT.

These visits will likely last about 2.5 to 3 hours.

**\*Missed or rescheduled treatment visits:** Because there may be a benefit from a single treatment session at any point during the study, subjects who miss or need to reschedule treatment visits will be eligible to complete their missed visit at any point prior to Month 3 procedures.

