## **10.4 Early Termination/Withdrawal Visit**

Subjects who are either withdrawn or terminated early from the study will have one final visit to report adverse events.

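### A PI withdrawal for undefined progressive disease ends cognitive follow-up, so ADCS-PACC can be lost because of the decline it measures; separating stopping stimulation from leaving the study is a cheap improvement

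*Combined protocol and SAP*

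**What the plan says.** Section 8.6 states that the PI "may discontinue or withdraw a subject from the study for the following reasons at his/her discretion". One listed reason is "There is evidence of progressive disease or unacceptable toxicity". The documents give no definition, scale, threshold or assessor for progression. Treated subjects who are then withdrawn are not replaced.

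Three places say what happens next:

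- Section 8.6: "The study team will attempt to obtain the following information from subjects following early termination or withdrawal: Adverse events and reason for withdrawal".
- Section 10.4: "Subjects who are either withdrawn or terminated early from the study will have one final visit to report adverse events".
- Section 10.1, Study Calendar: the "Early Withdrawal" column is marked for concomitant medications, physical exam, vital signs and adverse events. The rows for the cognitive battery and the study partner questionnaires are marked only at Baseline, Month 3 and Month 6.

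ADCS-PACC at 3 and 6 months is a secondary endpoint (Sections 6.0 and 12.1). Section 10.1 (Cognitive Battery) names it as the primary outcome of the future phase II trial. Section 9.4 sets threshold adherence as all stimulation and training sessions plus cognitive testing at 0, 3 and 6 months, and links this to the primary outcome, treatment completion.

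**The concern.** In amnestic MCI, progression of disease is largely cognitive decline, and that is what ADCS-PACC measures. A subject withdrawn from the study for that reason supplies no further score, so the missing value depends on what it would have been. Section 12.2 wants the pilot to give first estimates of variability and effect size for planning phase II. Losing the decliners would make an arm's mean look better and its spread smaller.

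The primary endpoint is also touched, through Section 9.4. A subject can receive every session, be withdrawn before Visit 17 or 18, and then miss the completion threshold only because the testing was not done.

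**Working it through.** The plan gives no figure of its own for this loss, so there is none to reproduce. The check covers what is lost at each point in time, and how large the loss could be.

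**1. What is lost, by time of withdrawal**

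| Withdrawn | 3-month score | 6-month score | Completion under Section 9.4 |
|---|---|---|---|
| During Visits 2-16 | lost | lost | fails in any case: sessions incomplete |
| After Visit 16, before Visit 17 | lost | lost | fails only for want of testing |
| After Visit 17, before Visit 18 | kept | lost | fails only for want of testing |

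One subject is 1/20 = 5% of the scores, and 5 percentage points of the completion rate in the last two rows.

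**2. How many subjects**

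Inputs: 20 subjects, 10 per arm, about 6 months each (Section 3.1); conversion from MCI to AD of 10 to 15% per year (Section 5.1). A constant rate is assumed.

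Risk over t years: p = 1 - (1 - r)^t.

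- t = 0.5: r = 0.10 gives 5.13%, x 20 = 1.03; r = 0.15 gives 7.80%, x 20 = 1.56.
- t = 0.25: 2.60% and 3.98%, x 20 = 0.52 and 0.80.
- Chance of at least one converter in 6 months, 1 - (1 - p)^20: 0.65 to 0.80.
- If the PI withdraws half of the 6-month converters: 0.51 to 0.78 of 20.

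The dropout assumption in Section 3.1 is 10% x 20 = 2 subjects, so the 6-month count lies within it. The calendar windows (4 weeks either way on the later blocks, 8 weeks either way on Month 6) can lengthen follow-up. At an assumed 9 months, 1 - 0.90^0.75 = 7.6% and 1 - 0.85^0.75 = 11.5%, or 1.5 to 2.3 of 20.

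**3. Effect of losing one low scorer**

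Simulation of 400,000 pairs of arms of 10 standard normal scores, with one subject lost from one arm:

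| Subject lost | Shift in that arm's mean | Pooled variance (true value 1) |
|---|---|---|
| Lowest scorer | +0.172 SD | 0.888 |
| Random one of the lowest three | +0.119 SD | 0.966 |

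For scale:

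- Standard error of the arm difference = sqrt(2/10) = 0.447 SD. The shifts are 0.119/0.447 = 27% and 0.172/0.447 = 38% of it.
- Relative standard error of a pooled variance on 18 df = sqrt(2/18) = 33%. The falls of 3.4% and 11.2% are about 0.10 and 0.34 of it.

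**4. Effect between arms**

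Both arms have the same conversion risk (5.13% or 7.80%), every converter is withdrawn, and the converters are always the arm's lowest scorers, which is an extreme case. Each arm's mean rises by 0.084 to 0.128 SD. The arm difference moves by -0.001 to +0.001 SD. The pooled variance falls to 0.895 to 0.848, still under half of its standard error. With half of the converters withdrawn, the means rise by 0.044 to 0.066 SD, the difference moves by 0.00, and the variance is 0.945 to 0.919.

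**The case against.** The strongest reply is that the clause reads as generic wording and that the disease-specific text leans the other way. Sections 8.2 and 10.1 (Decisional Capacity) let a subject who loses capacity stay in through a representative, with assent. Such a protocol hardly plans to remove people for ordinary decline. Nor is a battery, partner questionnaire or diagnostic review scheduled between Baseline and Visit 17. The only check is this: "On Mondays prior to CT and Fridays after CT, subjects will be assessed on competency and ability to perform the CT". Conversion would most naturally surface at Visit 17, when the 3-month score is already in hand. After that no visit falls before Visit 18 and no stimulation is left to stop. Section 12.4 adds that consenting patients are followed regardless of compliance and that loss to follow-up will be examined in sensitivity analyses.

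Much of this stands: it makes heavy use of the clause unlikely. It does not close the gap. The capacity provisions do not limit the discretion in Section 8.6. The Section 12.4 text is written for a future phase II trial and applies here only where suitable. It speaks of noncompliance rather than withdrawal by the PI, and its sensitivity analyses are unspecified and cannot recover scores never collected. The same section would also exclude data from non-adherent participants.

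A reader might infer that the clause biases the treatment comparison, or that decliners will be removed as a matter of course. The documents support neither. Use is discretionary, nothing suggests different use by arm, and with equal conversion the expected shift in the arm difference is zero.

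**Conclusion.** The gap is real and its consequences are small. As written, a PI acting within Section 8.6 can end cognitive follow-up because a subject is declining, and no other provision obtains the score. The primary endpoint is touched only for subjects withdrawn after Visit 16; earlier withdrawal makes them non-completers either way. It would therefore be wrong to call the completion rate compromised.

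The 1.0 to 1.6 of 20 is an upper bound for this route only if progression means conversion to AD, every converter is withdrawn, and the nominal 6 months holds. A broader reading of progression could catch more, but the documents give no rate for that. The shifts of 0.12 to 0.17 SD assume normal scores and a lost subject among the arm's lowest three. All are well within sampling error for 10 per arm. The point is an optional improvement, worth making because uncollected scores cannot be recovered and the visits and tests already exist.

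**What to change.** - **Section 8.6:** separate stopping HD-tDCS or sham sessions from leaving the study, for every PI-discretion reason. A rule limited to progression could be bypassed by the reason covering subjects who are no longer appropriate candidates. The decision on when to stop stimulation stays with the PI.
- **Visits 17 and 18:** ask stopped subjects to attend the cognitive and partner assessments, with consent or assent as in Sections 8.2 and 10.1 and with MRI optional.
- **Section 10.4 and the Early Withdrawal column:** for those who decline these visits, add the four ADCS-PACC components and the partner questionnaires. Report these off-schedule scores as supportive, not as 3- or 6-month values.
- **Section 12.4:** state that follow-up of all consenting patients applies to this pilot, and that the exclusion of non-adherent participants' data (written around 12-month testing and sham CT) does not.

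**Cost:** a short amendment, with no change to sample size. Section 10.2 puts Visit 17 at about 6 hours including MRI and Visit 18 at about 4, so a subject stopped during treatment would be asked for up to 6 + 4 = 10 hours, less without MRI. The payments in Section 8.5 would apply. The burden falls on perhaps one or two subjects who are worsening, so attendance must be voluntary, and some will decline.
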